225 randomization sequence sealed in an envelope.

226 **5.4 Blinding**

227 Study medications are known by both investigators and subjects. However,
228 independent clinical events committee is blinded to the treatment allocation.

229

230

231

232 Table 1: Study procedure table

| | Baseline | Visit 1 30 days | Visit 2 6 months | Visit 3 12 months |
|--------------------------------------|----------|--------------------|---------------------|----------------------|
| window | | ±7d | ±14d | ±30d |
| Informed consent | X | | | |
| Inclusion/exclusion criteria | X | | | |
| Randomization | X | | | |
| Medical history/demographic features | X | | | |
| Vital signs | X | | | |
| Routine blood and urine test | X | | | |
| Biochemical test | X | | | |
| CK/CKMB and troponin T | X | | | |
| Activated clotting time | X | | | |
| 12- leader electrocardiogram | X | | | |
| Important clinical symptoms | X | X | X | X |
| Clinical evaluation | X | X | X | X |
| Adjunctive medications | X | X | X | X |
| Coronary angiography | X | | | |
| Adverse cardiac events recording | | X | X | X |
| Adverse events recording | | X | X | X |

233 **6. Study population:**

234 **6.1 Target population:**

235 2100 patients who meet the inclusion criteria and receive study medications
236 before coronary angiography.

237 **6.2 Inclusion criteria**

238 (1) Patients aged from 18~80 years, male or female;

239 (2) AMI (STEMI or NSTEMI) patients with planned emergency PCI.

240 ● STEMI within 12 hours after symptom onset or within 12~24 hours with ongoing
241 chest pain, continuous ST segment elevation or new left bundle block.

242 ● NSTEMI within 72 hours after symptom onset.

243 (3) Staged revascularization for non-culprit vessel should be performed after 30 days.

244 (4) Antiplatelet agents (aspirin and clopidogrel, both loading and maintenance dose)
245 are given before PCI per guidelines.

246 (5) Subjects or legal representatives voluntarily participated and signed informed
247 consent, willing to accept study medications and clinical follow-ups.

248 **6.3 Exclusion criteria:**

249 (1) Patients not suitable for PCI; thrombolytic therapy administered before
250 randomization; cardiogenic shock;

251 (2) Any anticoagulant (heparin/LMWH, fondaparinux, warfarin or bivalirudin) or
252 tirofiban administered within 48 hours before randomization;

253 (3) Active or recent major bleeding or bleeding predisposition, including retinal or

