465 medical records.

466 • To ensure all errors and missing data are corrected or illustrated and signed
467 by the investigator.

468 • To ensure each therapeutic change, concomitant medication and complication
469 is recorded accurately.

470 • To ensure that all patient withdrawals or loss of follow-up are recorded in the
471 CRF.

472 • To ensure that all AEs are recorded and all SAEs are reported per standard
473 procedure.

474 • To ensure that the delivery, storage and recycling of study drugs abide to
475 regulatory requirements and are recorded.

476

477 **12. Statistical analysis**

478 BRIGHT is a prospective, multicenter, randomized, open label, active controlled
479 trial. AMI patients with planned emergency PCI will be enrolled and randomly
480 assigned to be treated with bivalirudin, heparin alone or heparin plus tirofiban.

481 Analysis for primary endpoint will be performed at the time that 30 day follow-up for
482 all subjects are completed. Analysis for secondary endpoints will be performed when
483 12-month follow-up are completed.

484 **12.1 Sample size calculation**

485 The primary endpoint is 30-day NACE, a composite of all-cause death,
486 reinfarction, ischemia driven TVR, stroke or any bleeding. Incidence of primary
487 endpoint will be compared between bivalirudin group and two control groups
488 sequentially. Only when both p values of two step tests (bivalirudin versus heparin
489 alone and bivalirudin versus heparin plus tirofiban) are less than 0.05, then the

490 conclusions of bivalirudin being superior to controls will be accepted.

491 The study hypothesis is that bivalirudin is superior to both heparin alone and
492 heparin plus tirofiban on 30-day NACE.

493 $H_0: P_B = P_C$

494 $H_1: P_B \neq P_C, \alpha = 0.05$ (two-sided)

495 P_B denotes NACE rate in the bivalirudin group, P_C NACE rate in the control group.

496 Assuming a 30-day NACE rate of 11.5% in the heparin alone group and 12.1%
497 in the heparin plus tirofiban group, allowing for 5% lost to follow-up, with a
498 two-sided alpha of 0.05, 700 patients per group would provide >90% power to
499 demonstrate a 45% reduction with bivalirudin for each comparison. Enrollment of
500 2,100 total patients (~700 per group) was therefore planned.

501

502 **12.2 Analysis populations**

503 All primary and major secondary endpoints will be analyzed both on an
504 intent-to-treat basis (all patients analyzed as part of their assigned treatment group)

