505 and on a per protocol basis (patients analyzed as part of their assigned treatment group
506 only if they actually received their assigned treatment). The primary statistical
507 analyses will be by intent-to-treat.

508 • **Intention-to-treat (ITT) set:** Patients who meet the study inclusion criteria, sign
509 the written informed consent and receive study medications after randomization
510 and have any assessment for the primary endpoint will be included in the ITT set.
511 ITT set will be used as baseline characteristics and endpoint analysis.

512 • **Per protocol (PP) set:** Patients with a successful procedure and complete
513 follow-up information will be included in the PP set.

514

515 **12.3 Statistical method**

516 Data will be analyzed using SPSS V19.0 software package. Two sided test with
517 alpha level of 0.05 will be used.

518 Baseline demographic and clinical variables will be summarized for each of the
519 treatment groups for the ITT set. All continuous variables will be summarized using
520 means, standard deviations, medians, interquartile ranges, minimums and maximum

521 values and two-sided 95% confidence intervals. Categorical variables will be
522 summarized using frequencies and percentages with two-sided exact 95% confidence
523 intervals. P-values comparing the two treatment groups will be presented for
524 descriptive purposes. Continuous data will be summarized using mean and standard
525 deviation and compared using Student's t-test or one-way ANOVA. Time-to-event data
526 were compared with the log-rank test.

527 Pre-specified subgroups for analysis include gender, age, type of AMI, heart
528 failure, diabetes, anemia, renal insufficiency, arterial access, multivessel disease,
529 history of cardiovascular events, high bleeding risk, and PCI for left anterior
530 descending coronary artery.

531

532 **13. Quality Control**

533 Sponsor shall appoint monitors to conduct systematic monitoring for the study in
534 accordance with GCP principles to ensure the study is carried out according to the
535 protocol and the case report form is identical with original data. The monitors should
536 also assess compliance corresponding to the regulations and protocol.

537 Investigators must ensure the integrity of the medical files. All study files will be
538 reviewed by the sponsor and monitors. Monitors should ensure the following: the

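### Optional improvement: pre-specified covariate adjustment of the 30-day NACE comparisons would recover about 1 to 4 points of the power to win both tests

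*Protocol*

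**What the plan says.** Section 12.1 states that the incidence of the primary "endpoint will be compared between bivalirudin group and two control groups" in sequence. Superiority is accepted only if both p values are below 0.05. The null hypothesis equates P_B and P_C, the NACE rates in the bivalirudin and control groups.

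The sample size uses control rates of 11.5% and 12.1%, 5% loss to follow-up and a 45% reduction in each comparison: "two-sided alpha of 0.05, 700 patients per group would provide >90% power to" show that reduction. No covariate enters the calculation.

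Section 12.3 names the t-test and one-way ANOVA for continuous data, and says that time-to-event data "were compared with the log-rank test". It names no test for a binary endpoint. Baseline variables have two stated uses. They are summarised by treatment group, and some define subgroups: "Pre-specified subgroups for analysis include gender, age, type of AMI, heart" failure, diabetes, anaemia, renal insufficiency and others. Table 1 schedules "Medical history/demographic features" and blood tests at baseline. Section 5.3 describes block randomisation and mentions no stratification factor.

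**The concern.** Several of the factors that Section 12.3 selects for subgroups are known before randomisation and can be expected to predict NACE. As written, they play no part in the primary comparison. Adjusting for such factors removes outcome variation that they explain, and so shortens the confidence interval without adding patients.

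This matters more here than in a two-arm trial because both tests must succeed and both use the same bivalirudin arm. Power is stated for each comparison separately. The chance of meeting the trial's own success rule is smaller than that, so a modest gain in precision has some value.

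**Working it through.** **Inputs (Section 12.1).** Control rates 11.5% and 12.1%; 45% relative reduction; two-sided alpha 0.05; 700 per arm less 5% = 665 evaluable. One bivalirudin rate cannot be exactly 45% below both controls, so two cases are needed:
- 0.55 × 11.5% = 6.325%
- 0.55 × 12.1% = 6.655%

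**Step 1: reproduce the stated power.** With p̄ the mean of the two rates, s0 = √[2p̄(1−p̄)/n], s1 = √[(pC(1−pC) + pB(1−pB))/n] and power = Φ[(pC − pB − 1.96·s0)/s1]:
- 11.5% v 6.325%: s0 = 0.015625, s1 = 0.015561; (0.05175 − 0.030625)/0.015561 = 1.358, power 91.3%.
- 12.1% v 6.655%: s0 = 0.015987, s1 = 0.015917; (0.05445 − 0.031334)/0.015917 = 1.452, power 92.7%.

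The stated figure of more than 90% per comparison holds without adjustment.

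**Step 2: power to win both tests.** The two statistics share the bivalirudin arm, so their correlation is [pB(1−pB)/n]/(s1·s1′), where s1 and s1′ belong to the two comparisons. Joint power is the bivariate normal probability.
- pB = 6.325%: single powers 91.3% and 95.4%; correlation 0.059249/665 ÷ (0.015561 × 0.015781) = 0.363; joint power 87.9%.
- pB = 6.655%: single powers 86.8% and 92.7%; correlation 0.374; joint power about 82% (0.8195).

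Without adjustment, 90% joint power needs 706 evaluable per arm (706/0.95, so 744 enrolled) in the first case and 814 (857 enrolled) in the second.

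**Step 3: effect of adjustment.** Variances are multiplied by (1 − R²). R² is an assumption, because the Protocol gives no prognostic strength. At an event rate of about 9%, R² of 0.02, 0.05 and 0.09 corresponds to a C-statistic of about 0.63, 0.70 and 0.75.

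| Assumed variance cut | Joint power, pB = 6.325% | Joint power, pB = 6.655% |
|---|---|---|
| none | 87.9% | 82.0% |
| 2% | 88.7% | 82.9% |
| 5% | 89.8% | 84.2% |
| 10% | 91.5% | 86.5% |

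The gains are 0.8, 1.9 and 3.6 points in the first case and 0.9, 2.2 and 4.5 in the second. A 5% cut is worth 665/0.95 = 700 evaluable patients per arm, so it offsets the planned loss to follow-up. Even a 15% cut gives only 88.7% in the second case.

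**Step 4: simulation at 6.325%, 11.5% and 12.1%, 665 per arm.**
- Five normal covariates, standardised risk difference, 3,000 trials per setting. At C = 0.60, 0.65, 0.70 and 0.75, variance falls by about 2%, 4%, 6% and 10%. Joint power moves from 88.7, 87.8, 88.5 and 88.7% to 89.4, 88.9, 90.0 and 91.6%. Type I error at C = 0.70 is 4.7% to 5.2%.
- One continuous and seven binary covariates with assumed prevalences, 2,000 trials per setting. Joint power moves from 88.1 to 88.5% at C = 0.60, from 87.7 to 89.2% at C = 0.67, and from 88.0 to 90.7% at C = 0.73.
- A further run with the same covariate mix cut variance by about 3%, 6% and 12% at C = 0.63, 0.70 and 0.77. Type I error stayed near 5%, and no power gain was detectable at C = 0.63.

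The Monte Carlo standard error is about 0.6 points at 3,000 trials, as large as the smallest gains.

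**The case against.** The strongest case against raising this is that it rests on silence. The Protocol names no primary test, the choice of model and covariates is commonly left to a statistical analysis plan, and that plan is not at hand. Most of this stands, and it is why the point is optional. What remains is that Sections 12.1 and 12.3 do describe a comparison of incidences, sized without covariates, and give baseline factors other roles only.

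A reader might infer four stronger things. The documents support none of them.
- **That an unadjusted test is prescribed.** The t-test, ANOVA and log-rank test in Section 12.3 are assigned to other data types. Hypotheses on P_B and P_C are also compatible with a standardised risk difference.
- **That the power statement is wrong.** It is made per comparison and is met without adjustment.
- **That chance imbalance makes the raw comparison invalid.** Under randomisation it is unbiased, and its standard error already allows for chance imbalance. Adjustment improves precision; it does not repair a bias.
- **That missing adjustment explains the joint-power shortfall.** Most of the shortfall comes from sizing each comparison separately.

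The size of the gain is also open to doubt. NACE includes any bleeding, down to BARC type 1. The exclusions (age over 80, cardiogenic shock, eGFR below 30, haemoglobin below 10 g/dL) narrow several candidate covariates. Prognostic strength could lie at the weak end.

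**Conclusion.** The point holds as an inexpensive improvement in efficiency. No stated figure is wrong and no invalidity is shown. Power to meet the both-tests rule is about 88% or 82%, depending on the bivalirudin rate. Pre-specified adjustment would add about 1 to 4 points (at most 4.5 in the table above) if the covariates cut variance by 2% to 10%. At a C-statistic near 0.60 the gain may be too small to detect. These figures rest on the planning rates of Section 12.1, 5% loss to follow-up and an assumed prognostic strength that the Protocol does not supply. If the bivalirudin rate is 6.655%, adjustment does not bring joint power to 90% at any strength considered.

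**What to change.** In Sections 12.1 and 12.3, state that each primary comparison is a covariate-adjusted test of 30-day NACE. One suitable form is a risk difference standardised from a logistic model, which keeps the meaning of P_B versus P_C. Fix a short covariate list in advance: age, sex, AMI type, heart failure, diabetes, renal insufficiency, anaemia and prior cardiovascular events. Define each from information that predates randomisation, because the baseline column of Table 1 also contains angiography.

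Leave out arterial access, multivessel disease and treated vessel. Sections 5.2 and 5.3 place randomisation and study drug before angiography, so these factors are settled after allocation in an open-label trial. Keep the unadjusted comparison as supportive, and report joint power beside the per-comparison figure.

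The cost is Protocol wording, a rule for missing baseline values, a little more analysis work, and possibly software beyond the SPSS V19.0 named in Section 12.3 for the standardised estimate. No extra patients or visits are needed.

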254 vitreous hemorrhage within one month, GI or urinary track hemorrhage within 3
255 months, intracranial hemorrhage within 6 months or cerebral infarction within 3
256 months;

257 (4) Patients at high risk of secondary bleeding, including active gastric ulcer,
258 ulcerative colitis, intracranial aneurysm, etc.;

259 (5) Major surgery (including ophthalmologic operation or neurosurgery) within 1
260 month;

261 (6) Clinical syndrome suspicious for aortic dissection, pericarditis or endocarditis;

262 (7) Uncontrolled blood pressure (>180/110 mmHg);

263 (8) Known hemoglobin <10 g/dL or platelet count <100 × 10⁹/L;

-
- 264 (9) Aminotransferase level >3x the upper limit of normal;
265 10) Severe renal insufficiency (eGFR<30 mL/min/1.73m²);
266 (11) History of heparin induced thrombocytopenia;
267 (12) Known allergy to study medications or device (heparin, bivalirudin, tirofiban,
268 aspirin, clopidogrel, stainless steel, contrast medium or hirudin) or allergic
269 constitution;
270 (13) Patient pregnant or lactating, or planned pregnant within 1 year;
271 (14) Study subjects with poor compliance judged by investigators or patient ever
272 participated in another clinical trial and has not completed the follow-up to the
273 primary endpoint.

274

275 **6.4 Criteria of patient removal, treatment discontinuation and drop out**

276 **6.4.1 Criteria of removal**

277 Patient should be removed if:

- 278 • Misdiagnosis.
- 279 • Without any record of physical or laboratory test results.
- 280 • Do not meet the inclusion criteria or meet at least one exclusion criteria.

281 The reason of removal should be written down and the case report form (CRF) should
282 be preserved for audit check. Removal patients will not be included in the efficacy
283 analysis but could be included in the safety analysis if there are any records regarding
284 efficacy or safety.

285 **6.4.2 Criteria of treatment discontinuation**

286 Discontinuation of any study medication is defined as stopping experimental
287 treatment. The reason of discontinuation should be clearly noted in the original
288 medical records and CRF.

289 Treatment should be discontinued if:

- 290 • Patient withdrawal of informed consent.
- 291 • Intolerable side effects of study medications

-
- 292 • Severe allergy that cannot be relieved by anti-allergic therapy
 - 293 • Adverse events or abnormal laboratory test results indicating that
 - 294 continuation of treatment would be inappropriate.

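### The set labelled ITT for the primary analysis is a modified ITT set: it contradicts the protocol's own all-patients definition and lets randomised patients drop out of the NACE comparison after open-label allocation

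*Protocol*

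**What the plan says.** Protocol section 12.2 (Analysis populations) promises analysis on an "intent-to-treat basis (all patients analyzed as part of their assigned treatment group", alongside a per-protocol analysis, and states that the primary "analyses will be by intent-to-treat". The synopsis says the same.

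The bullet that follows in 12.2 defines the ITT set by conditions:

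- eligibility: "Patients who meet the study inclusion criteria, sign" is how the definition opens;
- consent and treatment: "the written informed consent and receive study medications after randomization";
- outcome: "and have any assessment for the primary endpoint will be included in the ITT set".

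The set is not a side analysis: "ITT set will be used as baseline characteristics and endpoint analysis".

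Section 6.4.1 (Criteria of removal) adds another rule. A patient is to be removed for misdiagnosis, for having no record at all of physical or laboratory results, or under this criterion: "Do not meet the inclusion criteria or meet at least one exclusion criteria". The consequence is explicit: "Removal patients will not be included in the efficacy" analysis. Such patients may enter the safety analysis if records exist.

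Section 5.4 states that investigators and subjects know the treatment and that the clinical events committee does not. Under 5.2 and 5.3, randomisation takes place in the catheterization laboratory straight after consent, and study drug is given there before angiography.

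**The concern.** An intention-to-treat comparison is protected by randomisation because nothing that happens after allocation decides who is counted. Two of the conditions in 12.2, receiving study drug and having an endpoint assessment, are post-randomisation events. The third, eligibility, is a baseline property. Even so, 6.4.1 does not say who judges a breach, by when, or whether without knowledge of allocation and outcome. In an open-label trial that leaves room for exclusion to depend on treatment or on what happened to the patient.

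The endpoint sharpens the point. NACE counts any bleeding as well as death, reinfarction, target vessel revascularisation and stroke. A patient who was randomised, dosed and then bled, but is later found to breach a criterion, disappears from the primary net-benefit comparison. Bivalirudin is the shared arm, so selective loss there would move both primary comparisons in the same direction.

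**Working it through.** **1. The rules side by side.**

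| Patient | 12.2, general statement | 12.2, ITT set | 6.4.1 |
|---|---|---|---|
| Randomised, no study drug | in | out | not addressed |
| Randomised, no endpoint assessment | in | out | not addressed, unless no records at all |
| Fails an inclusion criterion | in | out | out of efficacy |
| Meets an exclusion criterion only | in | in | out of efficacy |
| Misdiagnosed | in | out only if an inclusion criterion fails | out of efficacy |

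The general statement conflicts with both restrictions. The two restrictions also disagree with each other: 12.2 names only the inclusion criteria, while 6.4.1 adds the exclusion criteria. The consent condition removes nobody properly randomised, because consent comes first.

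**2. The protocol's own power figure.** Section 12.1 assumes control rates of 11.5% and 12.1%, a 45% reduction, 700 per group, 5% loss and two-sided alpha 0.05. So n = 700 × 0.95 = 665, and the bivalirudin rate is 0.55 × 11.5% = 6.325% or 0.55 × 12.1% = 6.655%. With

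Power = Φ{ [ (pC − pB) − 1.96·√(2p̄(1−p̄)/n) ] / √([pC(1−pC) + pB(1−pB)]/n) }

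the results are 91.3% and 92.7% (92.6% and 93.8% at n = 700). The stated power above 90% reproduces, so the sample size is not at issue.

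**3. How much selective removal could matter.** The protocol gives no removal rate and no risk for removed patients, so everything here is assumed: true NACE p = 12% in both arms (between the two planning rates), 700 per arm, and a share e removed from the bivalirudin arm only, with event risk r.

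Retained bivalirudin rate: p′ = (p − e·r)/(1 − e), on 700(1 − e) patients.

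Chance of falsely favouring bivalirudin in one comparison: Φ{ [ (p − p′) − 1.96·SE₀ ] / SE₁ }, where SE₀ is the pooled and SE₁ the unpooled standard error.

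Worked case, e = 3%, r = 50%: 21 patients and 10.5 expected events are removed, so p′ = (84 − 10.5)/679 = 10.8%. Difference 0.01175, SE₀ 0.01713, SE₁ 0.01712; Φ(−1.275) = 10.1%.

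| Removed | Risk in those removed | Retained rate | Relative risk | False favour, one comparison |
|---|---|---|---|---|
| 3% | 12% (average) | 12.0% | 1.00 | 2.5% |
| 3% | 24% (twice) | 11.6% | 0.97 | 4.0% |
| 3% | 50% | 10.8% | 0.90 | 10.1% |
| 5% | 12% | 12.0% | 1.00 | 2.5% |
| 5% | 24% | 11.4% | 0.95 | 5.5% |
| 5% | 50% | 10.0% | 0.83 | 21.7% |

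The direction can reverse. If the 21 removed had no events, the retained rate would be 84/679 = 12.4%, to the disadvantage of bivalirudin.

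**4. The two-test rule.** Section 12.1 accepts superiority only if both comparisons reach p < 0.05. If all three arms are truly equal, the two statistics share the bivalirudin arm and have correlation near 0.5. The joint false-claim rate is then about 0.5% nominally, about 3% with 3% removed at 50% risk, and about 10% with 5% removed at 50% risk. If one control is truly worse, the single-comparison rates in the table are the relevant ones.

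**5. What including everyone costs.** Suppose a share of the bivalirudin arm is restored at the control rate, diluting the effect.

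| Restored | Power vs heparin (700 / 665 per arm) | Power vs heparin plus tirofiban (700 / 665 per arm) |
|---|---|---|
| 2% | 91.4% / 90.0% | 92.8% / 91.5% |
| 5% | 89.5% / 87.9% | 91.1% / 89.6% |

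**The case against.** The best defence is that few patients would be affected and that safeguards exist. Drug is given in the room where randomisation takes place, so untreated patients may be rare. Any assessment is a low bar, and an early death is itself an endpoint. Event adjudication is blinded, reasons for removal must be recorded with the case report form kept for audit, and removed patients may appear in the safety analysis. All of this stands as a limit on the likely scale. None of it puts a removed patient back into the primary NACE comparison: the events committee classifies events and is given no role in deciding who is analysed. A separate SAP might redefine the set, but that would not cure protocol text that contradicts itself.

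A reader might infer more than the protocol supports:

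- **That misdiagnosis comes to light only at angiography, or that renal and liver exclusions surface after a bleed.** Table 1 schedules ECG, cardiac markers and biochemistry at baseline and does not say whether results precede randomisation. Late discovery is possible, not stated.
- **That unblinded staff choose who is counted.** Section 6.4.1 does not say who decides or when. The fault is that this is left open.
- **That the error rate is 10% or 22%.** Those figures need removals from one arm only and an event risk above four times the assumed average. With average-risk removals there is no inflation, and with low-risk removals the shift goes the other way.

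**Conclusion.** The point holds as a contradiction in the definition of the primary analysis set. Section 12.2 states an all-patients principle and then fixes a narrower set, and 6.4.1 narrows it again on different grounds. What would be analysed is a modified ITT set under the name ITT, in an open-label trial with no safeguard on the removal decision. That is an error in what is written, not a detail left for later.

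Bias in the primary comparison is possible; whether it occurs, how large it is and which way it runs cannot be derived from the protocol. Under the one-arm assumptions above, the chance of falsely favouring bivalirudin in one comparison runs from 2.5% (no inflation) to 10.1% with 3% removed, and from 2.5% to 21.7% with 5% removed. The joint rate is lower when all arms are equal. Confidence is high in the contradiction and much lower in any particular size of effect.

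**What to change.** - In 12.2, define the ITT set as every randomised patient, analysed in the assigned arm regardless of eligibility, drug received or final diagnosis, using all available follow-up. Delete the eligibility, treatment and assessment conditions.
- In 6.4.1, make removal affect only the per-protocol set, and align its criteria with 12.2.
- Keep the present set if wanted, but call it modified ITT and use it as a secondary or sensitivity analysis.

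The cost is wording in two sections and a slightly diluted estimate. If 2% of the bivalirudin arm is restored at the control rate, power stays at about 90% or more for each comparison even at 665 per arm. At 5% it falls to 87.9% and 89.6%.
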